#### 6. SAFETY

All safety analyses will be based on the safety analysis set based on actual treatment received, unless otherwise specified.

For all continuous safety variables, descriptive statistics will include the N, mean, standard deviation, median, minimum, and maximum. Categorical variables will be summarized using frequency counts and percentages.

#### 6.1. Adverse Events

The verbatim terms used in the case report form (CRF) by investigators to identify adverse events will be coded using the Medical Dictionary for Regulatory Activities (MedDRA). Any AE occurring at or after the initial administration of study agent through the day of last dose is considered to be treatment emergent. If the event occurs on the day of the initial administration of study agent, and either event time or time of administration are missing, then the event will be assumed to be treatment emergent. If the event date is recorded as partial or completely missing, then the event will be considered to be treatment emergent unless it is known to be prior to the first administration of study agent based on partial onset date or resolution date. All reported treatment-emergent adverse events will be included in the analysis.

For each adverse event, the percentage of subjects who experience at least 1 occurrence of the given event will be summarized by treatment group.

Summary tables will be provided for:

- Overall summary of TEAEs
- TEAEs by SOC and PT

- TEAEs by SOC, PT, and severity (Mild, Moderate and Severe)
- TEAEs by SOC, PT, and NCI-CTCAE toxicity grade (for non-hematological AEs (using NCI-CTCAE Version 4)) TEAEs by SOC, PT, and IWCLL toxicity grade (for hematologic AEs (using IWCLL 2008 criteria))
- TEAEs by SOC, PT, and relationship to study agent (Not Related, Doubtful, Possible, Probable, Very Likely or Related [possible, probably, Very Likely] and Non-related)
- Serious TEAEs by SOC and PT
- Treatment related TEAEs by SOC, PT, and toxicity grade >= 3
- Treatment related serious TEAEs by SOC and PT
- TEAEs leading to discontinuation of study agent by SOC and PT
- AEs leading to death by SOC and PT

In addition to the summary tables, listings will be provided for subjects who had:

- Any TEAEs
- Serious TEAEs (SAEs)
- Severe TEAEs
- Treatment related TEAEs
- TEAEs leading to discontinuation of study agent
- AEs leading to Death

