#### **Parameters of Interest**

#### **Primary Endpoint:**

• The number and type of AEs reported by the investigator or the patient

The safety variables to be analysed include AEs and clinical laboratory tests

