#### **Exploratory Endpoints**

- Proportion of participants experiencing clinical response as per assessment criteria defined in section 9.1
- Change from baseline in patient-reported outcomes as per EORTC QLQ C-30 and FACIT Fatigue

The safety analysis population will include all subjects who sign the ICF and receive at least one dose of ImbruvicaTM. The verbatim terms used by participating physicians to document AEs in the CRF will be coded using the Medical Dictionary for Regulatory Activities (MedDRA). For each adverse event, the percentage of subjects who experience at least 1 occurrence of the given event will be summarized. Adverse events and serious adverse events will be summarized for the study duration by body system, preferred term, intensity, and relationship to ImbruvicaTM using descriptive statistics. Where appropriate, additional summaries, listings, or narratives may be provided for any deaths, serious adverse events, or any adverse events of clinical interest. Changes from baseline to the worst AE grade experienced by a patient during the study will be provided as shift tables. Results of investigations data including vital signs, if any, will be summarized using descriptive statistics.

All subjects who have received at least one dose of ImbruvicaTM and have completed one post-treatment PRO assessment will be considered for exploratory analysis. Exploratory endpoints will be summarized using descriptive statistics. Shift tables will be provided to determine the change in reported outcomes from baseline (Enrolment Visit) until Visit 8 /EOT.

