#### 11.4. Safety Analyses

# **Adverse Events**

The verbatim terms used in the CRF by investigators to identify adverse events will be coded using the Medical Dictionary for Regulatory Activities (MedDRA). Treatment-emergent adverse events are adverse events with onset during the treatment phase or that are a consequence of a pre-existing condition that has worsened since baseline. All reported adverse events will be included in the analysis. For each adverse event, the percentage of subjects who experience at least 1 occurrence of the given event will be summarized by treatment group.

Summaries, listings, datasets, or subject narratives may be provided, as appropriate, for those subjects who die, who discontinue treatment due to an adverse event, or who experience a severe or a serious adverse event.

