## 12.1. Definitions

#### 12.1.1. Adverse Event Definitions and Classifications

#### **Adverse Event**

An adverse event is any untoward medical occurrence in a clinical study subject administered a medicinal (investigational or non-investigational) product. An adverse event does not necessarily have a causal relationship with the treatment. An adverse event can therefore be any unfavorable and unintended sign (including an abnormal finding), symptom, or disease temporally associated with the use of a medicinal (investigational or non-investigational) product, whether or not related to that medicinal (investigational or non-investigational) product. (Definition per International Conference on Harmonisation [ICH])

This includes any occurrence that is new in onset or aggravated in severity or frequency from the baseline condition, or abnormal results of diagnostic procedures, including laboratory test abnormalities.

Note: The sponsor collects adverse events starting with the signing of the ICF (refer to Section 12.3.1. All Adverse Events, for time of last adverse event recording).

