### 12.3. Procedures

In this phase IV clinical study, ImbruvicaTM is the Janssen product under study.

The sponsor will provide appropriate pharmacovigilance training to the participating site personnel. The sponsor assumes responsibility for appropriate reporting of (serious) AEs and significant safety information originating from the data collected for Janssen medicinal products to the regulatory authorities. All collected AEs will be summarized in the final study report.

The names (and corresponding telephone numbers) of the individuals who should be contacted regarding product safety issues and/or quality issues are listed on the contact information page(s), which is/are provided separately.

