#### **Primary Endpoint**

• The number and type of TEAEs reported by the investigator or the patient.

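### The SAP replaces the protocol's AE endpoint with TEAEs ending on the day of last dose, so dated non-fatal AEs after a subject stops ibrutinib enter no AE table

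*SAP*

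**What the plan says.** **Protocol.** The Synopsis gives the primary endpoint as "The number and type of AEs reported by the investigator or the patient". Section 11.4 states: "All reported adverse events will be included in the analysis". The safety paragraph of the Synopsis adds "Adverse events and serious adverse events will be summarized for the study duration by body system, preferred term, intensity, and relationship" to ibrutinib, and section 12.3 says: "All collected AEs will be summarized in the final study report". On the start of collection, section 12.1.1 notes: "The sponsor collects adverse events starting with the signing of the ICF". Footnote f of the Time and Events Schedule continues collection to 30 days after last use within the study. It gives the purpose of that follow-up as finding drug-related AEs, new or ongoing, and any SAE whatever its cause.

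**SAP.** Sections 1.1 and 1.4 keep the objective of estimating AE incidence. Section 2.3 words the primary endpoint as "The number and type of TEAEs reported by the investigator or the patient". Section 6.1 sets the window: "Any AE occurring at or after the initial administration of study agent through the day of last dose is considered to be treatment emergent". It then says: "All reported treatment-emergent adverse events will be included in the analysis". Of the summary tables listed in 6.1, only the one for AEs leading to death is not restricted to TEAEs. An AE with a partial or missing date counts as treatment emergent unless it is known to precede first dose. Section 2 says that all study data will be listed. Last dose is not defined for subjects who go on taking ibrutinib after Visit 8, which the protocol Synopsis and section 3.1 allow.

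**The concern.** AE incidence is this study's only primary output, so the rule for which events count is central. The protocol sets up a 30-day follow-up to find late drug-related events and SAEs, but the SAP's tables leave them out. A subject who stops because of toxicity and has a non-fatal SAE two weeks later would be missing from the incidence, seriousness, grade and relationship tables for that event. Subject narratives are optional under protocol 11.4, so someone reading only the tables might not learn of the event. Neither document explains the change from AEs to TEAEs.

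**Working it through.** There is no stated figure to reproduce. The sample size of 75 comes from a committee recommendation, and no test is planned. The check is a comparison of texts followed by an illustration of size.

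**1. Where an event goes under SAP 6.1**

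| Event | AE summary table? |
|---|---|
| Dated, first dose through day of last dose | Yes |
| Dated, non-fatal, after last dose | None; general listing only |
| Date missing, or partial and not known to precede first dose | Yes, as a TEAE, even if it began after last dose |
| Fatal AE, any time | Yes, in the table of AEs leading to death |
| Dated, non-fatal, between consent and first dose | None; general listing only |

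The second and third rows show the inconsistency. The date rule tests only against first dose, so a poorly dated late event is counted and a well-dated one is not. The last row is minor. Screening and enrolment are one Day 1 visit, so few such events are expected, and their omission does not bias on-drug incidence.

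**2. Share of collection time left untabulated**

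Let d be days on drug and take the 30 days of follow-up in footnote f. The share of post-first-dose collection time is 30/(d + 30):

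- d = 360: 30/390 = 7.7%
- d = 180: 30/210 = 14.3%
- d = 90: 30/120 = 25.0%

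These are shares of time, not of events. On a 30-day follow-up they are upper bounds if a subsequent antineoplastic therapy ends collection earlier, as the Synopsis (Safety Assessment) and section 9.2 say.

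**3. Loss of incidence under one constant hazard (assumption)**

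Fix a single hazard through p, the incidence over 390 days. Risk over the collection period is 1 − (1 − p)^((d+30)/390), tabulated risk is 1 − (1 − p)^(d/390), and the loss is the difference. Two inputs are used: p = 10% (assumption), and p = 43.2%, the pooled SAE rate in the protocol's Safety Overview, borrowed only as an illustrative value.

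| d | p = 10%: full / tabulated / loss | p = 43.2%: full / tabulated / loss |
|---|---|---|
| 360 | 10.0 / 9.3 / 0.7 | 43.2 / 40.7 / 2.5 |
| 180 | 5.5 / 4.7 / 0.8 | 26.3 / 23.0 / 3.3 |
| 90 | 3.2 / 2.4 / 0.8 | 16.0 / 12.2 / 3.7 |

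Full and tabulated columns are percentages; losses are percentage points, taken before rounding. Each loss applies to a subject whose follow-up month is untabulated. The study-level loss is the average over all subjects, with zero for anyone whose window stays open.

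**4. Rough count of stoppers affected (assumption)**

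The Safety Overview gives 11.8% stopping for an AE; 0.118 × 75 = 8.85 subjects. If 10% to 50% of them had a dated non-fatal AE after last dose, that is 0.9 to 4.4 subjects. These are subjects with an omitted event, and they may still appear in the tables for another event.

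**The case against.** The best defence is that on-treatment TEAE reporting is ordinary practice, and that the protocol's own TEAE definition in section 11.4 also has no 30-day tail. That is right, and the definition is not the fault. But section 11.4 goes on to include all reported AEs, whereas the SAP does not.

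A second defence is that SAP 6.1 says the percentage of subjects will be summarized for each adverse event. That sentence follows the restriction to TEAEs, and no listed non-fatal table delivers it for other events.

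A third is that nothing is hidden. Fatal AEs are tabulated without restriction, all data are listed, and SAEs reach the sponsor within 24 hours. This limits the harm, but a listing gives no incidence, and the AE-specific listings in 6.1 are also confined to TEAEs and fatal AEs. Protocol 12.3 requires a summary.

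A fourth is that subjects who complete 12 months may continue ibrutinib. If last dose means the actual last dose, their follow-up month stays inside the window. This stands, so a reader should not infer that every completer loses a month of events; the SAP leaves that undecided. The point rests on subjects who stop.

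**Conclusion.** The contradiction is real and worth correcting. As written, the SAP does not deliver the protocol's primary endpoint for dated non-fatal AEs and SAEs after a subject stops ibrutinib. The bias in reported incidence is downward, of unknown and probably small size, and no test depends on it. The illustration gives losses of about 0.7 to 0.8 points at p = 10% and 2.5 to 3.7 points at p = 43.2%. It rests on the constant hazard, the chosen p and a full 30 days of collection. The Synopsis reports that infection, diarrhoea and bleeding were most prevalent in the first 6 months, which would make the loss after long treatment smaller.

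Three stronger readings are not supported:

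- A reader might apply 43.2% separately to each duration and infer a loss of 8.6 points for a subject who stops at 90 days (43.2% against 1 − 0.568^(90/120) = 34.6%). That gives this subject a hazard 390/120 = 3.25 times that of a completer. With one hazard the loss is 3.7 points.
- A reader might infer that omitting pre-dose events also lowers on-drug incidence. It does not, since those events precede exposure.
- A reader might infer that the protocol gives no usable end of AE collection. Footnote f and section 12.3.1 both lead to about the 30-day call, and the Synopsis end-of-treatment anchor falls close to it. What differs is whether new antineoplastic therapy ends collection, and section 9.2's count from the end of an observation period that already includes the call.

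**What to change.** - **SAP 2.3:** restore the primary endpoint to the protocol's AEs.
- **SAP 6.1, tables:** keep the on-treatment TEAE tables. Add tables of all AEs and all SAEs, from consent to the end of protocol AE collection, by SOC, PT, grade and relationship. Flag events before first dose and after last dose so that they can be read separately.
- **SAP 6.1, last dose:** define the term. Follow-up-month events in subjects still taking ibrutinib should be counted in the all-AE tables and flagged as on drug. Simply equating it with the last study dose would push those events out of the retained TEAE tables.
- **SAP 6.1, dates:** apply the end of the window to partially dated events where the partial date allows it.
- **Late related SAEs:** list separately those reported after the 30 days under protocol 9.2.
- **Secondary, protocol:** reconcile the Synopsis (Safety Assessment), footnote f, section 9.2 and section 12.3.1 on the anchor for the end of AE collection and on whether subsequent antineoplastic therapy ends it. Use that single end in the tables.

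The cost is a few SAP sentences, one protocol clarification and extra tables on data already collected. Reported incidences may be slightly higher.

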#### **Safety Overview**

Pooled safety data for subjects treated with ibrutinib monotherapy in 9 studies that have completed primary analysis as of the cutoff date for this Investigator's Brochure update (6 April 2015) (Studies 04753, 1102, 1112, 1117, 1104, MCL2001, 1106, 1118E, and JPN-101) are summarized below. The data presented also include subjects enrolled in Studies 1112 (N=57) and CLL3001 (N=90) who crossed over from ofatumumab or placebo, respectively, to receive treatment with ibrutinib monotherapy after progression and/or positive interim analysis results. Median duration on treatment was 8.3 months (range: 0.0 to 32.3 months).

Treatment-emergent AEs in more than 10% of subjects receiving ibrutinib as monotherapy (N=1071) The most frequently reported treatment-emergent AEs were diarrhea, fatigue, nausea, cough, anemia, pyrexia, and neutropenia.

Treatment-emergent AEs assessed as related to ibrutinib by the investigators in more than 5% of subjects receiving ibrutinib as monotherapy (N=1071). Adverse events that were considered by the investigator to be related to ibrutinib monotherapy were reported in 75.5% of subjects. The most frequently reported AEs related to ibrutinib were diarrhea, fatigue, neutropenia, and nausea.

Treatment-emergent AEs of Grade 3 or 4 in severity in more than 2% of subjects receiving ibrutinib as monotherapy (N=1071). Adverse events of Grade 3 or 4 were reported in 49.3% of subjects. The most commonly reported Grade 3 or 4 AEs that were hematologic in nature were neutropenia, thrombocytopenia, and anemia. Pneumonia, hypertension, and atrial fibrillation were the most frequently reported nonhematologic Grade 3 or 4 AEs.

The incidence of treatment-emergent SAEs reported in more than 1% of subjects receiving ibrutinib as monotherapy (N=1071). Serious AEs were reported in 43.2% of subjects. The most frequently reported SAEs were pneumonia, atrial fibrillation, febrile neutropenia, and pyrexia. The most frequently reported SAEs (any grade) that were considered related to ibrutinib were pneumonia, atrial fibrillation, and febrile neutropenia.

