## **Overall Rationale**

Post-marketing phase IV clinical trial is useful in identifying new safety issues and trends, which were not observed in previously conducted clinical studies. The data obtained from the present study will help to understand the safety profile of ibrutinib in a real-world Indian scenario compared with that obtained in a controlled clinical environment. The objective of the present study is to address the mandatory regulatory requirement regarding conduct of study in Indian population to monitor the adverse events with ImbruvicaTM (Ibrutinib capsule 140 mg). The study will assess the safety of ImbruvicaTM prescribed as per locally approved Prescribing Information in Indian patients of CLL or MCL who have received at least one prior therapy or CLL with 17p deletion.

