# 1.3. Statistical Hypotheses for Trial Objectives

No formal hypothesis testing will be conducted. Data will be summarized using descriptive statistics. Continuous variables will be summarized using the number of observations, mean, SD, median, and range as appropriate. Categorical values will be summarized using the number of observations and percentages as appropriate. Exploratory endpoints will be summarized using descriptive statistics.

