# 1.4. Sample Size Justification

The primary objective of this study is to estimate the incidence of AEs in Indian subjects under actual conditions of use of ImbruvicaTM. A sample size of 75 subjects is as per the recommendations of Subject Expert Committee (Oncology & Hematology) made in its 70th meeting held on 23rd May 2018 at Central Drugs Standard Control Organization HQ, New Delhi communicated vide F.N. 12-10/2017-DC (Pt-Johnson-snd).

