# 5.1.3. Proportion of subjects experiencing clinical response as per assessment criteria

Following are the response categories to be assessed:

- Complete Response (CR)
- Partial Response (PR)

- Stable Disease (SD)
- Disease Progressive (PD)

Analysis: The number and percentage of subjects will be provided in the following response categories: CR, PR, SD, PD. Data for response assessment will be listed individually for each subject at each visit for efficacy analysis set. The proportion of subjects who achieved the best response of (CR+PR) and its 95% confidence interval (CI) will be analyzed on efficacy analysis set.

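### The primary aim is to estimate AE incidence, but SAP 6.1 plans only crude percentages, with no confidence interval and no allowance for differing time on drug

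*SAP*

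**What the plan says.** SAP 1.4 gives the primary objective as being "to estimate the incidence of AEs in Indian subjects under actual conditions of use". On size it says only that "A sample size of 75 subjects is as per the recommendations of Subject Expert Committee", with no precision target, and SAP 1.3 adds that "No formal hypothesis testing will be conducted".

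For the primary outcome, SAP 6.1 states that for each adverse event "the percentage of subjects who experience at least 1 occurrence of the given event will be summarized by treatment group". The opening of SAP 6 limits categorical safety data to counts and percentages. Protocol 11.4 and the protocol synopsis go no further.

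Exploratory outcomes are treated more fully. SAP 5.1.3 plans the CR+PR proportion, and "its 95% confidence interval (CI) will be analyzed on efficacy analysis set". SAP 5.1.4 plans Kaplan-Meier PFS with 95% CIs for the median and for the rates at 6 and 12 months.

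On time at risk:
- Protocol 3.1 has each subject treated for 12 months or until progression, whichever comes first.
- SAP 6.1 counts an AE as treatment-emergent only up to the day of last dose.
- SAP 4.4 summarises treatment duration and average daily dose, but separately from AEs.

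On context, the protocol's Overall Rationale says that the data will help in understanding the "safety profile of ibrutinib in a real-world Indian scenario compared with that obtained in a controlled clinical environment". The synopsis says much the same. The Safety Overview gives pooled monotherapy results for 1071 subjects, with a median treatment duration of 8.3 months and a range of 0.0 to 32.3 months.

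**The concern.** An estimate with no statement of precision only partly meets an aim of estimation. The sample size has no statistical derivation, so an interval is the only place where the report could show what 75 subjects can support. This matters most for rare events. The study is meant to help find new safety issues, and a count of zero is informative only with its upper limit.

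The second gap is time at risk. The percentage of subjects with at least one event rises with time on drug. Here that time differs between subjects and stops at 12 months. In the pooled data it runs from 0.0 to 32.3 months. A crude percentage from this study therefore cannot be set fairly beside a pooled one, and a difference between them could come from exposure alone. The SAP already applies a time-to-event method to an exploratory endpoint, so the primary outcome receives the simpler analysis.

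**Working it through.** **The plan's own figure.** The sample size of 75 is attributed to a committee recommendation. No alpha, power, effect size or precision target is stated, so there is nothing to reproduce and no ground for calling 75 wrong.

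**1. Precision at n = 75.** The method is the exact (Clopper-Pearson) two-sided 95% interval. For x events in n subjects, the lower limit is the 0.025 quantile of Beta(x, n−x+1) and the upper limit is the 0.975 quantile of Beta(x+1, n−x). The event counts are illustrative: the pooled percentages in the protocol's Safety Overview, multiplied by 75 and rounded.

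| Category | Pooled | x/75 | Exact 95% CI |
|---|---|---|---|
| Serious AE | 43.2% | 32 (42.7%) | 31.3% to 54.6% |
| Grade 3 or 4 AE | 49.3% | 37 (49.3%) | 37.6% to 61.1% |
| AE leading to discontinuation | 11.8% | 9 (12.0%) | 5.6% to 21.6% |
| Fatal AE | 9.3% | 7 (9.3%) | 3.8% to 18.3% |
| No events seen | – | 0 | 0% to 4.8% |

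The serious AE interval is 54.6 − 31.3 = 23.3 points wide.

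**2. Effect of time on drug, with underlying risk unchanged.** Inputs: 43.2% with a serious AE and a median of 8.3 months, both from the Safety Overview. Assumptions: every pooled subject was exposed for 8.3 months, and time to first serious AE is Weibull with shape k, where k = 1 is a constant hazard and k = 0.5 is strongly front-loaded. The documents do not give k. Values below 1 are plausible because Protocol 3.1 (Treatment Period) reports that infection, diarrhoea and bleeding were most prevalent in the first 6 months.

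- Cumulative hazard at 8.3 months: H = −ln(1 − 0.432) = 0.5656.
- Incidence by month T: 1 − exp(−H × (T/8.3)^k).
- T = 6, k = 1: 1 − exp(−0.5656 × 0.723) = 33.6%.
- T = 6, k = 0.5: 1 − exp(−0.5656 × 0.850) = 38.2%.
- T = 12, k = 1: 1 − exp(−0.5656 × 1.446) = 55.9%.
- T = 12, k = 0.5: 1 − exp(−0.5656 × 1.202) = 49.3%.

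**3. Which direction is likely here?** Twelve months is a ceiling. A rough achieved exposure follows from the protocol's background figures, assuming exponential stopping for progression and for AEs:

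- Stopping for AEs: 11.8% by 8.3 months gives −ln(0.882)/8.3 = 0.0151 per month.
- Progression or death in MCL: 6-month PFS of 63% gives −ln(0.63)/6 = 0.0770 per month.
- Progression or death in CLL: 12-month PFS of 88% at 420 mg gives −ln(0.88)/12 = 0.0107 per month.
- Mean exposure capped at 12 months is (1 − exp(−12h))/h, where h is the sum of the two rates.
- MCL: h = 0.0921, giving 7.3 months. CLL: h = 0.0258, giving 10.3 months.

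With these means in the formula of step 2, the serious AE figure is about 39% (MCL) to 50% (CLL) for k = 1, and about 41% to 47% for k = 0.5. Both ranges straddle the pooled 43.2%. Using a mean in place of the full spread of exposures is itself an approximation, good enough to show that the direction is open.

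**The case against.** The strongest reply is that this is a descriptive single-arm study with no hypothesis tests, and that leaving out an interval biases no estimate. Counts will be shown with percentages, so a reader can work out an exact interval. Treatment duration is tabulated and TEAEs are listed. All of this is true, and it limits the harm. It does not explain why exploratory response and PFS get intervals and the primary outcome does not. Nor can time at risk be recovered from the summary tables, because duration is summarised apart from events.

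A reader might also infer that the SAP plans a comparison with earlier trials and that longer treatment here will produce a false excess. The documents support neither reading. The comparison is a general statement of rationale: it does not name the pooled data set, and no objective, endpoint or table carries it out. The direction is not fixed either. Reading 12 months as typical exposure sets a ceiling beside an achieved median, and the MCL/CLL mix is not specified. Step 3 shows that the figure could fall below 43.2% as well as above it.

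The objection also stands against one possible remedy. A single rate per 100 patient-months assumes a roughly constant hazard, which the protocol's own account of infection, diarrhoea and bleeding argues against. The documents give no pooled person-time with which to compare it.

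**Conclusion.** The point holds in this form: the primary aim is estimation, and the only planned AE estimator is a crude percentage with no interval and no allowance for time on drug. The first part rests on the text alone. Its size is an unreported exact 95% interval about 23 points wide for serious AEs if the pooled rate recurs, and an upper limit of 4.8% when no event is seen.

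The second part is a limit on interpretation. Exposure alone could move the pooled 43.2% to about 34% to 38% at 6 months or 49% to 56% at 12 months. That range rests on treating 8.3 months as every pooled subject's exposure and on an assumed Weibull shape of 0.5 to 1. It shows that unadjusted percentages cannot fairly be set beside the pooled data. It does not show that this study will overstate risk. Disease mix and setting also differ, and adjusting for exposure would not remove those differences.

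This is a worthwhile SAP improvement and does not threaten the study's validity.

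**What to change.** In SAP 6.1:

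1. Add exact (Clopper-Pearson) 95% CIs for the proportion of subjects with any TEAE, and with serious, Grade 3 or higher, related, discontinuation-leading and fatal AEs. Do the same for haemorrhage, infection and atrial fibrillation, which the protocol's Safety Overview discusses as risks.
2. For the same rows, add the cumulative incidence of first event at 6 and 12 months with 95% CIs, stating how death and stopping drug are handled. Alternatively, give exposure-adjusted rates by period (0 to 6 and over 6 to 12 months). Either is preferable to one overall person-time rate.
3. State that any reading against earlier trials is descriptive and depends on exposure and disease mix.

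The cost is some programming and wider tables. Dosing start and stop dates are already collected (Protocol 6, SAP 4.4), and the onset-date rules in SAP 6.1 presuppose AE dates. No new data, visits or subjects are needed.
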